9. RESEARCH DESIGN AND METHODS

Overview: This pilot trial is a Phase IV, 12-week, single center, randomized, double blind, parallel group comparison of low (0.5 mg twice daily with slower titration over one full week) versus standard dose (1.0 mg twice daily with standard titration) varenicline in SMI individuals with DSM-V BD or SSD with a 12-week, post-treatment follow-up (see Figure 3 for study design). The 16 visits after screening (Weeks 0-24) will take place using the guidelines developed by the UCSD Office of the Vice Chancellor for Research. Participants will be screened, randomized and follow the protocol according to the Research Ramp-Up phase under which the university is operating at that time of (i.e., orange, yellow, or green).

Full participation includes 14 treatment visits and 3 follow up visits. All in-person visits will take place at Pac-TARC. In addition to testing low dose varenicline in SMI smokers for the first time, three other innovative design features are incorporated to try to improve medication tolerability and short-term quit rates. 1) Plasma will be obtained at baseline to measure participants' NMR and to identify slow versus normal nicotine metabolisers. 2) A flexible quit date (between days 8-35) will be employed allowing varenicline preloading to occur prior to the TQD. 3) Ten sessions of ACT for smoking cessation will be delivered by trained counselors first in 7 in-person sessions followed by 3 sessions delivered via telephone to all participants. Randomization of participants will occur in a 1 (low dose) to 1 (standard dose) ratio and participants will be balanced on diagnosis (BD vs SSD), gender, race (White vs. non-White) and whether or not they are taking antiepileptic medications (e.g., carbamazepine) as mood stabilizers (20) which, like the demographic/ethnic factors (11,26) can influence CYP2A6 activity and affect the NMR. Volunteered, observed and solicited NPSAEs will be assessed using standardized procedures developed in EAGLES and our other prior work (4,27). However, going beyond EAGLES, we will also assess participants' tobacco withdrawal symptoms, urges to smoke, sleep disturbances, self-efficacy & confidence to quit, and satisfaction with the protocol elements. To further extend EAGLES, we will include more "real world" participants who are somewhat less psychiatrically stable and who have comorbid substance use disorders (SUDs) in early remission.

Figure 3. Study Design – ACTSLOW Pilot Trial

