⁷Smoking Self-Efficacy Questionnaire (SEQ-12); ⁸Confidence to Quit Scale; ⁹Hospital Anxiety and Depression Scale (HADS); ¹⁰Altman Self-Rating Mania Scale (ASRM); ¹¹Columbia-Suicide Severity Rating Scale (C-SSRS); ¹²Neuropsychiatric Adverse Events Interview (NAEI); ¹³Client Satisfaction Questionnaire-8 (CSQ-8)

Phase 1 (Red Phase):

Screening Visit (Week 0). If the University reverts to the Red Phase again, potential participants will not be recruited, screened or enrolled. Participants who are currently enrolled in the study, however, will continue to be followed.

Baseline Visit (Week 0). We will randomize already screened and consented participants remotely during this phase. Eligible participants will continue participation for a baseline evaluation that will take approximately 2-3 hours by telephone (via HIPAA compliant Doximity). Although the method of administration varies by Research Ramp-Up phase (see below), the following standardized questionnaires will be collected for all phases of

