operation, at baseline and throughout the study: **Minnesota Nicotine Withdrawal Scale** (MNWS; 31) to monitor symptoms of tobacco withdrawal; **Questionnaire of Smoking Urges-Brief** (QSU-Brief; 32) to measure cravings to smoke; the **TLFB for Alcohol and Drug Use** (33,24); the **Nicotine Use Inventory** (NUI; 4, 27) is a brief questionnaire that has been used throughout the varenicline Phase III-IV trials that monitors smoking rates and probes for other forms of nicotine use including e-cigarettes, hookah, cigars, etc; the **Hospital Anxiety and Depression Scale** (HADS; 35) is comprised of two separate 7-item self-report questions assessing anxiety and depressive symptoms, respectively; the **Altman Self-Rating Mania Scale** (ASRM; 36) is a 5-item self-rating mania scale with a scoring range from 0-20 that assesses symptoms of mania and hypomania; the **Columbia-Suicide Severity Rating Scale** (C-SSRS; 37) is a semi-structured interview conducted by trained raters to monitor suicide ideation and behaviors; the **Insomnia Severity Index** (ISI; 38) is a reliable and valid 7-item self-report measure to evaluate perceived sleep difficulties; the **Avoidance and Inflexibility Scale** (AIS; 41) is a 27-item questionnaire measuring changes in acceptance-based processes of smoking cessation based on this technique's hypothesized mechanism of action; the **Neuropsychiatric Adverse Events Interview** (NAEI) is a 25-item questionnaire that was used in EAGLES (4) and our prior work (27) to probe for neuropsychiatric complaints that might qualify as adverse events in a clinical trial; an **Assessment of General AEs** using standard operating procedures to record AEs according to the Medical Dictionary for Regulatory Activities version 18.0 (MedDRA; 44) – derived preferred terms; and the **Self Efficacy Questionnaire** (SEQ-12; 42) and **Confidence to Quit Scale** (43) measuring participants' self-efficacy and confidence to quit smoking. Study medication will be dispensed to participants by mail per VMRF pharmacy's shipping protocol with instructions on its use. Participants will also have their first session of ACT session (see below) at their week 0 baseline visit. All assessments will be performed by telephone (on HIPAA compliant Doximity) as scheduled with the exception of vitals, urine or blood collection, and exhaled CO which will not be collected during this Red phase.

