Treatment & Follow-up Visits (Weeks 1-12). Table 3 illustrates the schedule of assessments for all follow-up visits, which will be done by telephone via Doximity during this phase. On Day 8 (week 1) participants will pick a day between 8 and 35 to be their target quit date considering that one goal of the study is to have participants take varenicline for several weeks before trying to quit to maximize effectiveness. Study weeks 1, 3, and 5 will take approximately 30 minutes to complete as participants will have 30-minute ACT sessions, as described below. Study weeks 2, 4, and 6 will take approximately 1 hour as participants will have ACT sessions and questionnaires to complete (see table 3). Study weeks 8, 10, and 12 will take 30-45 minutes to complete as participants will not have ACT on these visits but will complete questionnaires. Telephone visits for study weeks 7, 9, and 11 will take ~35 minutes, as the last ACT sessions will be completed during these visits. In addition to the questionnaires given at baseline described above the following questionnaires will be given during the treatment phase: the **Client Satisfaction Questionnaire – 8** (CSQ-8; 39) is a standardized measure of treatment satisfaction that has been used widely across mental health services (40) and in smoking cessation research with varenicline preloading (18) and the **ACT Treatment Satisfaction Questionnaire** (ACT-TSQ) measures treatment satisfaction with ACT counseling using two force-choice response items and a Likert scale (9).

Non-Treatment Follow-up Visits (weeks 13-24): Following discontinuation of the medication participants will be followed every 4 weeks until conclusion of the study assessing mood, any suicidal thinking, and nicotine or other drug use. Visits for study weeks 16, 20 and 24 will be done via Doximity and take approximately 30-45 minutes.

Phase 2 (Orange Phase):

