Baseline Visit (Week 0). Eligible participants will return to Pac-TARC following screening for a baseline evaluation that will take approximately 2-3 hours. First, two 4mL tubes of blood will be collected via venipuncture for use in determining the NMR outcome variable and as a backup sample stored at Pac-TARC and baseline blood pressure and heart rate will be measured. Next, the following standardized questionnaires will be collected at baseline and throughout the study: **Minnesota Nicotine Withdrawal Scale** (MNWS; 31) to monitor symptoms of tobacco withdrawal; **Questionnaire of Smoking Urges-Brief** (QSU-Brief; 32) to measure cravings to smoke; the **TLFB for Alcohol and Drug Use** (33,24); the **Nicotine Use Inventory** (NUI; 4, 27) is a brief questionnaire that has been used throughout the varenicline Phase III-IV trials that monitors smoking rates and probes for other forms of nicotine use including e-cigarettes, hookah, cigars, etc; the **Hospital Anxiety and Depression Scale** (HADS; 35) is comprised of two separate 7-item self-report questions assessing anxiety and depressive symptoms, respectively; the **Altman Self-Rating Mania Scale** (ASRM; 36) is a 5-item self-rating mania scale with a scoring range from 0-20 that assesses symptoms of mania and hypomania; the **Columbia-Suicide Severity Rating Scale** (C-SSRS; 37) is a semi-structured interview conducted by trained raters to monitor suicide ideation and behaviors; the **Insomnia Severity Index** (ISI; 38) is a reliable and valid 7-item self-report measure to evaluate perceived sleep difficulties; the **Avoidance and Inflexibility Scale** (AIS; 41) is a 27-item questionnaire measuring changes in acceptance-based processes of smoking cessation based on this technique's hypothesized mechanism of action; the **Neuropsychiatric Adverse Events Interview** (NAEI) is a 25-item questionnaire that was used in EAGLES (4) and our prior work (27) to probe for neuropsychiatric complaints that might qualify as adverse events in a clinical trial; an **Assessment of General AEs** using standard operating procedures to record AEs according to the Medical Dictionary for Regulatory Activities version 18.0 (MedDRA; 44) – derived preferred terms; and the **Self Efficacy Questionnaire** (SEQ-12; 42) and **Confidence to Quit Scale** (43) measuring participants' self-efficacy and confidence to quit smoking. Participants will also have their first session of ACT session (see below) at their week 0 baseline visit.

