10. HUMAN SUBJECTS

Sixty men and women with DSM-V BD (Type I or Type II, N = 30) or SSD (schizophrenia or schizoaffective disorder, N = 30) and who are chronic smokers will be recruited to participate in this pilot trial at Pac-TARC, which is a research center housed within the UCSD Department of Psychiatry. With an anticipated 33% screen failure rate, we anticipate screening up to 90 participants to accrue the sample. Each group will include ~ 50% women and individuals of any ethnic background are eligible to participate. Based on our prior work recruiting for EAGLES in San Diego where 35% (182/523) of those phone-screened self-identified as BD or SSD smokers, we expect that the SMI smokers who call to inquire about the study will have demographic and clinical characteristics similar to those SMI smokers enrolled in EAGLES (e.g., ~47% female, 65% White). Also, like EAGLES, we expect BD and SSD smokers to have similar baseline smoking characteristics.

Inclusion Criteria

- 18-70 years of age
- Outpatients with a DSM-V diagnosis of BD or SSD
- Smoke at least 10 cigarettes per day and have an expired carbon monoxide (CO) breathalyzer of \geq 10 ppm at screening and baseline visits
- Are motivated to quit smoking by scoring 5 or higher on the Contemplation Ladder (28)
- Have access to a mental health provider should their condition worsen during study enrollment

Exclusion Criteria

- Females who are pregnant, planning to become pregnant, or lactating
- Test positive for any non-prescribed medications (e.g., opiates, benzodiazepines, psychostimulants) or illicit drugs excluding cannabis during screening
- Have made a suicide attempt or engaged in self-mutilatory behavior in the past year
- Meet criteria for another SUD in the past month
- In the investigators' judgement, are either psychiatrically (e.g., presently manic, hypomanic, acutely psychotic, depressed or suicidal) or medically (e.g., uncontrolled hypertension, angina) unstable to safely participate
- Are currently using any other form of treatment for smoking cessation

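### Red phase randomises already screened people without the baseline CO that eligibility requires or the NMR plasma that Aim 2 needs, and leaves week-12 and week-24 abstinence there impossible to confirm

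*Combined protocol and SAP*

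**What the plan says.** All references are to the combined protocol and SAP.

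- **Section 9, Phase 1 (Red Phase), Screening Visit.** In Red, "potential participants will not be recruited, screened or enrolled".
- **Section 9, Red Phase, Baseline Visit.** The next paragraph says: "We will randomize already screened and consented participants remotely during this phase". Assessments are by telephone, "with the exception of vitals, urine or blood collection, and exhaled CO which will not be collected during this Red phase".
- **Section 9, Overview.** The phases named for screening and randomising are orange, yellow and green. Red is not among them.
- **Section 10, Inclusion Criteria.** Expired CO must be at least "10 ppm at screening and baseline visits". No exception by phase is given.
- **NMR sampling.** The Overview says "Plasma will be obtained at baseline to measure" the ratio. The Yellow/Green baseline text says "two 4mL tubes of blood will be collected via venipuncture for use in determining the NMR outcome variable", and the Orange text does the same. Table 3 marks the NMR at week 0 only. No later or substitute draw is described.
- **Table 3** also marks a urine pregnancy test at week 0.
- **Section 9, Red Phase, later visits.** Table 3 governs the visits in weeks 1 to 12, "which will be done by telephone via Doximity during this phase". For follow-up, "Visits for study weeks 16, 20 and 24 will be done via Doximity".
- **Section 9, 2° Efficacy Outcome.** Seven-day point prevalence abstinence (PPA) at week 12 (secondary) and week 24 (tertiary) requires confirmation by expired CO and urine cotinine.

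**The concern.** The Red text cannot be followed together with the inclusion criteria, the Overview and Table 3. A person randomised under it has no baseline CO, so cannot be shown to meet a stated criterion. That person also has no NMR value, so cannot be placed in the comparison of slow metabolisers on standard dose with normal metabolisers on low dose. The plan states neither a waiver nor what happens when the NMR is missing.

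A related problem arises at the outcome visits. In Red neither confirmatory test can be done. The abstinence definition does not separate a test that was not done from a test that was failed. Applied literally, it scores a self-reported quitter as a smoker because of the operating phase. The observed rate is to be set against 28.2% at week 12 and 20.0% at week 24, so how untested people are classed affects how those comparisons read.

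**Working it through.** **1. Passages side by side**

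| Item due at baseline | Required by | In Red |
|---|---|---|
| Expired CO | Section 10, Inclusion Criteria | Not collected |
| NMR plasma | Section 9 Overview; Table 3, week 0 | Not collected |
| Urine pregnancy test | Table 3, week 0 | Not collected |
| A phase in which randomisation occurs | Section 9 Overview: orange, yellow, green | Red randomises |

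The screening CO does exist for these people, because Red takes only those already screened. The missing reading is the baseline one.

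**2. How many people the baseline gap reaches**

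Inputs: 4 randomised per month (Hypothesis 1a), a 15-month recruitment period (Sample Size Determination), and screening at week -2 with baseline at week 0 (Table 3). The plan's own sample size reproduces: 4 x 15 = 60.

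Screening stops in Red, so only people between the two visits are exposed, and this pool does not grow while Red lasts:

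- 4 per month x 0.5 month = 2 people per return to Red (1.8 at 4.345 weeks per month). 2/60 = 3.3%.
- If the gap were four weeks (an assumption): 4 x 4/4.345 = 3.7 people.
- Slower accrual gives proportionally fewer.

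**3. Effect on the Aim 2 contrast**

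With 30 per arm and 40% slow metabolisers (the Background figure for smokers without mental illness, assumed here):

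- Slow on standard dose: 30 x 0.40 = 12.
- Normal on low dose: 30 x 0.60 = 18.
- Total in the contrast: 30.
- Expected loss from 2 people without NMR: 2 x (0.5 x 0.40 + 0.5 x 0.60) = 1.0.

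The expected loss is 1 whatever the share of slow metabolisers, since the two terms always sum to 0.5.

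For precision, use SE(d) = sqrt[(n1 + n2)/(n1 n2) + d²/(2(n1 + n2))] and an 80% interval. At 30 per arm and d = 0.40 this gives 0.066 to 0.734, against the plan's 0.064 to 0.733. In the contrast itself:

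- 12 v 18: width 0.964.
- 11.6 v 17.4 (two NMR values missing): width 0.981.

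The loss of precision is slight.

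**4. Effect on abstinence**

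The plan gives no length for Red. At 4 randomised per month and full retention, about 4 week-12 visits fall due in each month of Red, and none of them can be confirmed.

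To show what the choice of rule can do, suppose 28.2% of those tested are abstinent and 20% of 60 are untested, from any cause. The 20% is the worst case that still meets the retention target in Hypothesis 1b:

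- Tested: 60 x 0.80 = 48.
- Untested left out: 28.2%.
- Untested counted as smoking: 28.2 x 48/60 = 22.6%.
- Difference: 5.6 points. At week 24, 20.0 x 48/60 = 16.0%, a difference of 4.0 points.

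For scale, the 95% half-width at n = 60 is 1.96 x sqrt(0.282 x 0.718/60) = 11.4 points.

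**The case against.** Red applies only if the University returns to it. The Red text says openly that CO, urine and blood are not taken, so it can be read as a deliberate exception for that phase. The people concerned had a CO reading at screening, and they are few. PPA is secondary or tertiary, Aim 2 is exploratory, no formal testing is planned, and the Sample Size section says the trial is not powered for clinical outcomes. All of this stands and keeps the weight low. It does not remove the conflict: the inclusion criterion names both visits, no exception is written, and the Overview leaves Red out.

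Four stronger readings are tempting, and the documents do not support them.

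- **That Red admits people whose smoking was never verified.** It does not. Only the second CO reading is missing.
- **That the plan leaves abstinence undefined in every phase.** The requirement of confirmation implies that an unconfirmed person is not abstinent. What is missing is the distinction between not measured and failed, which is a detail on a secondary endpoint.
- **That abstinence will be understated by 5.6 points.** That figure is an illustration at the floor of the retention target, and Sample Size Determination cites retention above 80% in earlier work. The plan does not say how the EAGLES 28.2% treated unconfirmed people. If they were counted as smoking there, doing the same here would compare like with like.
- **That the arms are biased against each other.** With 1:1 randomisation, Red should fall about equally on both, so the effect is mainly on the overall rate.

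**Conclusion.** The point holds as a minor one. The Red instructions conflict with the inclusion criteria, the Overview and Table 3. Following them enters people without a required baseline CO and without an NMR value. At target accrual and a two-week gap this is about 2 people per return to Red, and about 1 of the 30 expected in the NMR contrast, with little effect on its precision. These people still contribute adverse-event and feasibility data.

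People whose week-12 or week-24 visit falls in Red cannot be confirmed and, on a literal reading, are scored as smoking for a reason unrelated to their smoking. How many this affects cannot be computed, because the length of Red is not given.

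**What to change.** 1. **Reconcile the Red text with the Overview, the inclusion criteria and Table 3.** The preferable course is to defer randomisation in Red until the baseline CO, urine and NMR plasma can be obtained. The cost is a delay for about 2 people per return to Red, for as long as Red lasts. If Red randomisation is kept, write the exception into the criteria and the schedule. Leave people without an NMR value out of the NMR contrast only, and keep them in all feasibility and adverse-event summaries. The week-0 pregnancy test must be reconciled in the same amendment; how is for the sponsor to settle.
2. **Under 2° Efficacy Outcome, report verified 7-day PPA two ways at weeks 12 and 24:** among those tested, and with untested people counted as smoking. Give by arm the number untested because of the operating phase, separately from those lost to follow-up or who missed the visit.

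Both are changes of wording plus a few table rows. Neither needs new data.

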2° Efficacy Outcome: In keeping with the pilot nature of this trial, we will use 7-day point prevalence abstinence (PPA) at week 12 confirmed by expired CO levels ≥ 4 ppm and urine cotinine levels < 200 mg/ml as the secondary efficacy endpoint. We will continue to track smoking outcomes through week 24 using these same biochemical verification measures to assess 7-day PPA at week 24 as a tertiary outcome.

Other Secondary Outcome Measures: Our gathering of data on the MNWS, QSU-Brief, ISI, SEQ-12, Confidence to Quit Scale is exploratory in nature and is intended to provide preliminary information on the mechanism of action of combined varenicline and ACT in SMI smokers and their relation to NPSAEs. We will also explore ACT's effects on avoidance and inflexibility with the AIS at weeks 12 and 24.

Determination of the NMR: The ratio of trans-3'-hydroxycotinine (3HC) and cotinine (COT) will be measured in plasma using electrospray ionization liquid chromatography tandem mass spectrometry (ESI LC-MS/MS) technology adapted from the protocols described by Tanner et al. (45) and Lerman et al. (7). COT and 3HC in plasma will be determined by quantifying with standard deuterium labeled COT and 3HC, known as COT-d3 and 3HC-d3 (commercially available from Sigma-Aldrich). Plasma samples will be spiked with a known amount of COT-d3 and 3HC-d3, and samples will be subjected to MS to quantitate the endogenous levels of COT and 3HC by parallel reaction monitoring. LC-MS/MS will be performed on the high-resolution Orbitrap Q-Exactive LC -MS system located in the [name] lab in the Skaggs School of Pharmacy and Pharmaceutical Sciences. Standard plots of different amounts of deuterated and non-deuterated COT and 3HC standards into control plasma, followed by LC-MS/MS, will define the linear range of quantitative measurements, lower limit of detection, and reproducibility of replicate samples. Ratios of 3HC/COT will be calculated from quantitative MS data analyzed by the Skyline software. Reliability of these procedures in plasma is high with NMR measurements robust even to differences in analytic methods used by different laboratories (45). The NMR data will be compiled with the phenotypic data of this study to examine the relationship of NMR to NPSAEs and smoking cessation.

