To gather preliminary data on the NMR, the frequency distributions of the NMR values in this SMI sample will be compared with the published data from Lerman et al. (2015) in a large sample of NMI smokers that found a cutoff score of 0.31 as the demarcating point between slow (<0.31) and normal (including rapid) metabolisers. Based on this analysis, we will calculate Cohen's d effect sizes comparing slow metabolisers on standard dose vs. normal metabolisers on low dose, as well as standard deviations and CIs, for incidence of NPSAEs of any severity to examine the direction and magnitude of the effect. Secondary outcome measures will also be examined using the same methodologies including 7-day PPA at weeks 12 and 24, to guide future studies. Regarding the secondary efficacy outcomes, and anticipating possible quit-boosting effects from ACT and varenicline preloading, we predict 7-day PPA rates at week 12 will be at least comparable to those observed in varenicline-treated EAGLES SMI participants which was 28.2%, and that 7-day PPA rates at week 24 will be at least comparable to the 20.0% observed in EAGLES (unpublished data). To examine the possible confounding effect of variable lengths of abstinence depending on when participants first attempt to quit smoking within the quit window, we will examine the effect of a time factor (i.e., the number of days from the first dose of medication to the date of the first quit attempt) with the methodologies described above.

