Sample Size Determination: The aims of this pilot trial are to gather preliminary data or demonstrate proof of principle with potential for high impact within one or more stated research priorities of the funding agency. Thus, Aim 1 of the proposal addresses feasibility while Aim 2 is exploratory and begins to test the principle as to whether NMR influences NPSAE propensity and medication tolerability in SMI smokers by estimating effect sizes. The study is designed to provide preliminary data on the feasibility of a larger RCT that would further develop these novel pharmacotherapy approaches in SMI smokers. It is not powered to test clinical outcomes, thus, safety (incidence of NPSAEs) and efficacy (7-day PPA at week 12 and at week 24) outcome measures are considered secondary endpoints. In our group's previous work with varenicline in EAGLES (4) and another trial done in SMI smokers (49), we randomized ~80% of those screened and retained >80% of study participants. Similar retention rates were found in another pilot trial of varenicline in bipolar smokers (52) and in [name] preliminary study. Therefore, we expect that with N=60 we will be able to adequately determine the feasibility of the proposed study procedures.

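### The rule that verifies abstinence runs the wrong way on CO (4 ppm or more confirms quitting), and its cotinine limit, in mg/ml, can never be exceeded

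*Combined protocol and SAP*

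**What the plan says.** The efficacy endpoint is set out in section 9 under 2° Efficacy Outcome, which names 7-day abstinence at week 12 and gives the biochemical rule for it: "confirmed by expired CO levels ≥ 4 ppm and urine cotinine levels < 200 mg/ml". The next sentence carries the rule forward, "using these same biochemical verification measures to assess 7-day PPA at week 24 as a tertiary outcome". No other place in the document gives a CO cut-off for abstinence, or another cotinine limit or unit.

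CO also appears in section 10, Inclusion Criteria, where a participant must "have an expired carbon monoxide (CO) breathalyzer of \geq 10 ppm at screening and baseline visits". There a high reading qualifies someone as a current smoker.

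The Data Analytic Plan (section 9, Aim 2) sets the resulting rates against figures from an earlier trial. The week-12 rate is predicted to be "at least comparable to those observed in varenicline-treated EAGLES SMI participants which was 28.2" percent, and the plan predicts that "7-day PPA rates at week 24 will be at least comparable to the 20.0% observed in EAGLES". Abstinence at both time points is also to be examined by metaboliser and dose group.

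**The concern.** One sentence holds two separate faults, and correcting either leaves the other in place.

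The first is the direction of the CO test. A high CO admits a participant as a smoker and, under this rule, later certifies the same participant as a non-smoker. The sentence also conflicts with itself: its cotinine half treats a low value as evidence of abstinence, while its CO half treats a high value that way.

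The second is the cotinine unit. With the limit in mg/ml the test has no capacity to reject anyone.

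This is the only definition of the efficacy endpoint. It feeds the week-12 and week-24 abstinence rates, their comparison with 28.2% and 20.0%, and the analyses of abstinence by metaboliser and dose group that are meant to guide a larger trial. An error here does more than add noise, because it reverses the classification of the people whom biochemical verification exists to separate.

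**Working it through.** The plan derives no sample size, power or event count from this rule, so there is no figure of its own to reproduce. The check is a unit conversion, a logic table and a count of those exposed.

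**Inputs from the document**
- Confirmation rule: CO ≥ 4 ppm and urine cotinine < 200 mg/ml (section 9, 2° Efficacy Outcome).
- Entry level for current smokers: CO ≥ 10 ppm (section 10, Inclusion Criteria).
- Benchmark abstinence: 28.2% at week 12 and 20.0% at week 24 (section 9, Data Analytic Plan, Aim 2).
- Sample size: 60, with 30 per arm (section 9, Sample Size Determination).

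**Step 1: CO direction.** Anyone with CO ≥ 10 ppm also has CO ≥ 4 ppm. Every participant whose CO is still at the entry level therefore passes the CO test for abstinence.

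**Step 2: cotinine unit.** 1 mg = 1,000,000 ng, so 200 mg/ml = 200 × 1,000,000 = 200,000,000 ng/ml. The same limit is 200 g per litre. At an assumed urine output of 0.5 to 3 litres a day, reaching it would need 200 × 0.5 = 100 g to 200 × 3 = 600 g of cotinine a day. At an assumed 1 g per cigarette, 60 whole cigarettes weigh 60 g. The limit cannot be reached, so the test always passes.

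**Step 3: the rule applied.** The cotinine values below are illustrative and do not come from the document. The last column assumes that ng/ml was the intended unit.

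| CO (ppm) | Cotinine (ng/ml) | As written | CO < 4 and cotinine < 200 ng/ml |
|---|---|---|---|
| 0, 1, 2, 3 | 10, 100 | not confirmed | confirmed |
| 0, 1, 2, 3 | 500, 2,000, 10,000 | not confirmed | not confirmed |
| 4, 6, 10, 20, 30 | 10 to 10,000 | confirmed | not confirmed |

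As written, cotinine never changes the result. The rule reduces to self-reported abstinence plus CO ≥ 4 ppm.

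**Step 4: size.** If the benchmark rates held here and all 60 participants were assessed:
- Week 12: 0.282 × 60 = 16.9, about 17 quitters.
- Week 24: 0.200 × 60 = 12 quitters.

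None of these with CO below 4 ppm could be confirmed. If all of them had CO below 4 ppm, the confirmed rate among true quitters would be 0%.

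**The case against.** **It may be a text-reading artefact.** Each fault is about one character wide, and the text was read from PDF by a program. This cannot be fully excluded. However, the same symbol reads correctly elsewhere, for example in the minimum of 10 cigarettes per day under Participants in section 9. A misread sign would not explain the unit either, and two independent misreads in one line are unlikely.

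**It is an obvious slip in a secondary endpoint of a pilot.** The Sample Size Determination text says of the study, "It is not powered to test clinical outcomes". The feasibility aim, the main adverse-event contrast in Aim 2 and the sample size of 60 do not use this rule. That limits the reach of the error and stands. Even so, the lay summary in section 5 counts quitting among the major endpoints, and no other definition exists to fall back on. A silent correction at analysis would mean choosing the threshold, its boundary and its unit after the data are in hand.

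**The count of 17 is an assumption.** This is fair. The 28.2% is an unpublished rate from another trial, and the document does not say how it was verified. The count also assumes that everyone has a CO reading, yet neither CO nor urine is collected in the Red phase and most Orange-phase visits are remote.

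**Not every true quitter would fail.** Also fair. Section 10 exempts cannabis from the drug-test exclusion, so a tobacco quitter who smokes cannabis might stay at or above 4 ppm and pass. The statement holds for quitters with CO below 4 ppm.

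**Conclusion.** The concern holds. As written, the verification rule cannot measure abstinence. It rejects every self-reported quitter with CO below 4 ppm, accepts those whose breath test contradicts them, and makes no use of cotinine. The CO fault is shown by the document's own entry criterion and by the opposite direction of the cotinine half. The unit fault is shown by arithmetic: the limit is one million times the same number in ng/ml.

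The damage is confined to the week-12 (secondary) and week-24 (tertiary) abstinence outcomes and whatever is built on them. At the benchmark rates, and with complete assessment, that is about 17 and 12 of 60 participants. Those counts are conditional. The finding that the rule is inverted and its second test is empty does not depend on them.

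Two points rest on assumption: that ng/ml was the intended unit, which appears nowhere in the document, and that the printed sign is what the sponsor's file shows. The sentence must be corrected before any abstinence result is classified.

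**What to change.** Amend the 2° Efficacy Outcome text so that abstinence is confirmed by self-reported 7-day abstinence, expired CO < 4 ppm and urine cotinine < 200 ng/ml, and state that the corrected rule also applies at week 24. The sponsor should confirm the cotinine cut-off and unit against its assay. It should also confirm that a reading of exactly 4 ppm counts as not abstinent, which is what the complement of the printed rule implies.

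The cost is a one-sentence wording amendment with no new data collection. Two checks belong with it:
- Record numeric CO and cotinine values rather than pass or fail. Under Data Storage, urine is tested on collection and not kept, so a sample scored only against the wrong limit could not be scored again.
- State how abstinence is classed when a visit was remote and neither CO nor urine was obtained. Correcting the sentence does not settle those cases.
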